10. MEASUREMENT OF EFFECT

10.1. Efficacy Assessments (Antitumor Activity)

Tumor response assessments

All tumor assessments will be performed and analyzed based on RECIST v 1.1 (refer to Appendix 1 for details). Eligible subjects for this study must have measurable disease at Baseline, determined by the presence of at least one measurable target lesion. To assess best response (CR, PR, stable disease [SD], PD, not evaluable [NE]), each subject's overall tumor burden at Baseline will be compared with subsequent measurements of lesions. Tumor response is to be assessed every 9 weeks. The same modality and contrast agent should be used for each measurement.

Timing and Method of Tumor Assessments

Baseline tumor assessments must be performed within 21 days before the first infusion of study treatment during the Pretreatment Phase to confirm subject eligibility and to identify target and nontarget lesions to be followed during the study. Baseline tumor assessments will consist of radiographic evaluation (CT or MRI scans) of the chest, abdomen, pelvis, and any other areas of known or suspected disease, along with clinical assessment of skin lesions, if applicable, using a metric ruler in the field and measured using calipers. A bone scan should also be performed on all subjects within 6 weeks before the first infusion of study treatment.

Radiologic tumor assessments of the chest, abdomen, pelvis and other areas of known disease that are scanned at screening, or areas of newly suspected disease, must be performed every 9 weeks. During treatment, tumor assessments should be performed any time within 1 week of administration of the first dose of study treatment in the next treatment cycle. Tumor assessments may be performed sooner than every 9 weeks if there is symptomatic evidence of PD upon clinical examination of the subject.

For subjects with a possible PR or CR (according to RECIST v 1.1), changes in tumor measurements must be confirmed by repeat evaluations, to be performed not less than 4 weeks after the response criteria are first met. **The same imaging modality and image-acquisition protocol (including use or nonuse of i.v. contrast) should be used across all time points to allow consistent comparison of lesions.**

The preferred type of **CT scan** is a diagnostic quality spiral or multi-detector CT with i.v. and oral contrast. If iodinated i.v. contrast is contraindicated, it is recommended that the chest evaluation be done with noncontrast CT and the abdomen and pelvis evaluation be performed using either CT with oral contrast (without i.v. contrast) or MRI with gadolinium chelate i.v. contrast. Low-dose noncontrast CT transmission scans from a positron-emission tomography (PET)-CT combination scanner are **not** acceptable. Spiral/multidetector CT and MRI body scans should be performed using ≤ 5 mm contiguous slices. **Skin lesions** should be clinically assessed using a ruler with millimeter subdivisions in the field and measurement performed using calipers. Ultrasound and low-dose noncontrast CT transmission scans from a positron emission tomography-CT (PET-CT) combination scanner are **not** acceptable methods of radiographic tumor assessment. However, a fluorodeoxyglucose positron emission tomography (FDG-PET) scan, chest x-ray or skeletal x-ray that clearly demonstrates a new metastatic lesion may be used to document PD in lieu of the CT/MRI scans.

Post screening **bone scans** will be performed at treating physician discretion. Scans can also occur as clinically indicated for new symptoms or to confirm disease response. Radiological scans that were negative at baseline do not have to be repeated unless clinically indicated. The recommended bone scan technique is 99m-technetium-labeled methylene diphosphonate (99m-Tc-MDP) scintigraphy or whole-body bone MRI. If an alternative scanning method is used, it should be continued throughout the rest of the study.

The same methodology and scan acquisition techniques used at screening should be used throughout the study to ensure comparability.

A **brain scan** by CT or MRI will only be performed at treating physician discretion. Scans can also occur as clinically indicated for new symptoms or to confirm disease response. Radiological scans that were negative at baseline do not have to be repeated unless clinically indicated. Brain scans should be performed with contrast-enhanced CT or MRI with ≤ 5 -mm contiguous slices. **Skin lesions** should be clinically assessed using a metric ruler in the field and measured using calipers. If **subcutaneous masses or nodes** are palpable (e.g., bulky) and are assessable by both clinical and radiographic techniques, the radiographic (CT/MRI) technique should be used for the assessment of these lesions, whether target or nontarget.

If study treatment is discontinued due to radiographic evidence of PD, the subject does not have to undergo tumor assessments at the End-of-Treatment visit. Follow-up disease evaluation is not required for subjects who have radiographic evidence of PD at the time of discontinuation of treatment or for those subjects who withdraw consent before developing PD.

10.2. Baseline Identification of Target and Nontarget Lesions

At Baseline, the investigator is to select up to a total of five measurable lesions (two per organ) that are representative of all involved organs as **target lesions**. Target lesions are to be selected on the basis of their size (the lesion with the longest diameter) and suitability for accurate repeated measurements (either by imaging techniques or clinically). To be considered a **target lesion** at Baseline, the lesion must be measurable and have a minimum size of ≥ 10 mm in the longest diameter for non-lymph node lesions or ≥ 15 mm in the short-axis for a lymph node.

All other lesions (or sites of disease), both measurable and nonmeasurable, will be identified as **nontarget lesions** and will be recorded at Baseline. Nontarget lesions will be evaluated at the same assessment time points as target lesions. However, measurements will not be required, and these lesions will be followed as “present” or “absent.”

Refer to Appendix 1 for further details on the evaluation of target and nontarget lesions.

10.3. Primary efficacy variable/endpoint

The antitumor activity of eribulin mesylate monotherapy will be assessed by determining ORR based on RECIST v 1.1 (Appendix 1). For analysis purposes, ORR is defined as the proportion of subjects who achieve a CR plus those who achieve a PR. To be assigned a status of PR or CR, changes in tumor measurements must be confirmed by repeat evaluations, to be performed not less than 4 weeks after the response criteria are first met.

10.4. Secondary efficacy variables

The secondary efficacy endpoints for this study are time to first response, duration of response and PFS, defined as follows:

- Time to first response will be defined for subjects whose best overall response (OR) is a CR or PR. The time to first response will be measured from the date of first dose of study treatment until the earliest date that CR or PR is objectively documented.
- Duration of overall response will be defined for subjects whose best OR is CR or PR. The duration of OR will be measured from the time that response criteria for CR or PR (whichever is recorded first) are first met until the date that PD or death from any cause is first objectively documented). Subjects who do not have PD will be censored on the day of their last tumor assessment.
- Progression-free survival will be defined as the time from the date of the first dose of study treatment until the date of first documentation of PD or date of death from any cause (whichever occurs first). Subjects who die without reported PD are considered to have progressed on the day of their death. Subjects who are alive at the end of study without reported PD will be censored on the date of their last tumor assessment.

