14.4. Analysis of Secondary Efficacy Variables

Progression-free survival (PFS) will be analyzed using Kaplan-Meier product-limit estimates and presented separately for each cohort. Median PFS and the cumulative probability of PFS at 6 and 12 months will be presented with two sided 90% CIs derived using log(-log(survival)) methodology. Time to first response and duration of response will be summarized for the responders using the Kaplan-Meier method. The cumulative PFS, time to first response, and duration of response probabilities will be plotted over time. Median and first and third quartiles from Kaplan-Meier estimation for PFS, time to first response, and duration of response will be provided with 90% CIs.

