- In the case of SD, follow-up measurements must have met the SD criteria at least once after study entry at a minimum interval of 5 weeks for this protocol.

Table 4 Best Overall Response with Confirmation

Unconfirmed Response (First Time Point)	Confirmatory Response (Subsequent Time Point)	Best Overall Response of:
CR	CR	CR
CR	PR	SD, PD or PR ^a
CR	SD	SD or PD ^b
CR	PD	SD or PD ^b
CR	NE	SD or NE ^c
PR	CR	PR
PR	PR	PR
PR	SD	SD
PR	PD	SD ^b
PR	NE	SD ^c
NE	NE	NE

BL = baseline; CR = complete response; NE = not evaluable; PD = disease progression; PR = partial response; SD = stable disease

a: If a CR is truly met at first time point, then any reappearance of disease seen at a subsequent time point (including disease meeting PR criteria relative to BL) makes the disease PD at that time point

b: Classify response as SD, provided that confirmatory scan a minimum of 5 weeks later is still "SD." Otherwise, response classified as PD.

c: Classify response as SD, provided that confirmatory scan a minimum of 5 weeks later is still "SD." Otherwise, response classified as NE.

Duration of Overall Response

The duration of OR is measured from the date that measurement criteria are met for CR or PR (whichever status is recorded first) until the first date that recurrence or PD is objectively documented, taking as reference for PD the smallest sum LD recorded since the treatment started.

Duration of Stable Disease

Stable disease is measured from the start of the treatment until the criteria for PD are met, taking as reference the smallest sum LD recorded since the treatment started.

The clinical relevance of the duration of SD varies for different tumor types and grades. For this protocol, duration of stable disease is not being measured.

Response Review

For this Phase 2 study, response review will be performed at the site by appropriately qualified personnel (radiologist in conjunction with clinical investigator).

Reporting of Results

All subjects included in the study should be assessed for response to treatment, even if there are major protocol treatment deviations or if they are ineligible.

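### The duration-of-response censoring sentence in Section 10.4 does not exempt deaths; it conflicts with the event definition before it and, read literally, would bias the Kaplan-Meier duration upward

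*Combined protocol and SAP*

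**What the plan says.** Three places bear on how a responder's duration ends.

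- **Section 10.4, duration of overall response.** The clock runs from the first time response criteria are met "until the date that PD or death from any cause is first objectively documented". The next sentence gives the censoring rule: "Subjects who do not have PD will be censored on the day of their last tumor assessment".
- **Section 17.1 (Appendix 1), Duration of Overall Response.** The duration runs "until the first date that recurrence or PD is objectively documented". Death is not mentioned.
- **Section 14.4.** "Time to first response and duration of response will be summarized for the responders using the Kaplan-Meier method". The median and quartiles are to be reported with 90% confidence intervals. No event or censoring rule is given here.

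For comparison, the PFS bullet in Section 10.4 addresses the same situation directly: "Subjects who die without reported PD are considered to have progressed on the day of their death", and "Subjects who are alive at the end of study without reported PD will be censored on the date of their last tumor assessment".

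**The concern.** A responder who dies before progression is documented meets both sentences of the duration bullet. The first makes the death an event on its date. The second, read literally, censors the patient at the last scan. Scans are 9 weeks apart (Section 10.1), so the censoring date can precede the death by up to 9 weeks, or longer if scans were missed.

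Censoring in a Kaplan-Meier analysis assumes that the patient's response could have continued beyond that date. For a patient who died this is false, and the estimate is pushed upward. The same death would also be a PFS event and a censored duration, within one trial and one section.

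Such patients are plausible. Appendix 1 has a category for stopping treatment because of declining health without objective progression, and Section 5.7 lets treatment stop for progression judged clinically. Some of these patients could die before RECIST progression is recorded. In an open-label single-arm study, the choice between the two readings should not be left until the data are visible.

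**Working it through.** **1. The texts side by side, for a responder who dies without documented PD**

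| Source | Treatment of that death |
|---|---|
| 10.4, duration: event sentence | Event on the date of death |
| 10.4, duration: censoring sentence, read literally | Censored at last tumor assessment |
| Appendix 1, duration | Not an event; death not mentioned |
| 14.4 | Silent |
| 10.4, PFS | Event on the day of death; only living subjects censored |

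The plan states no figure for duration of response, so there is none to reproduce.

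**2. Number of responders.** Section 14.2 assumes response rates of 22% (TNBC) and 30% (HR-positive), with 45 patients in each cohort: 45 × 0.22 = 9.9 and 45 × 0.30 = 13.5, or about 10 to 14 per cohort. This takes duration to be reported by cohort. Section 14.4 says so for PFS but does not repeat it for duration.

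**3. Closed form.** Assume exponential durations with median M, and let d be the share of first events that are deaths without PD. Censoring those deaths at the time of death leaves the hazard (1 − d) × ln 2 / M, so the apparent median is M / (1 − d). With M = 6 months (assumed):

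- d = 5%: 6 / 0.95 = 6.3 months
- d = 10%: 6 / 0.90 = 6.7 months
- d = 20%: 6 / 0.80 = 7.5 months
- d = 30%: 6 / 0.70 = 8.6 months

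For k deaths among n responders, d = k/n and the inflation factor is n / (n − k). With n = 12 this is 12/11 = 1.09 for one death and 12/10 = 1.20 for two.

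**4. Small-sample simulation.** 20,000 samples of n exponential durations, true median 6 months. In each, k randomly chosen events are censored at the previous 63-day scan. The table gives the median of the Kaplan-Meier medians, in months. Two conventions are used where the curve equals exactly 0.5: take the first time it reaches 0.5 or less, or take the midpoint of the flat segment.

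| n | Convention | k = 0 | k = 1 | k = 2 | Change, k = 1 / k = 2 |
|---|---|---|---|---|---|
| 10 | first time | 5.2 | 6.0 | 7.0 | +15% / +35% |
| 12 | first time | 5.3 | 6.0 | 6.8 | +13% / +27% |
| 12 | midpoint | 6.1 | 6.4 | 7.1 | +6% / +17% |
| 13 | first time | 6.0 | 6.4 | 6.8 | +7% / +14% |
| 14 | first time | 5.4 | 6.0 | 6.7 | +11% / +24% |

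Percentages can differ by about a point from ratios of the rounded medians, and repeat runs differ by about 0.1 month. Over n = 10 to 14 and both conventions, the range is about +5% to +16% for one death and +13% to +35% for two. The closed-form values for n = 12 (+9% and +20%) lie inside these ranges.

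**5. Direction.** For n = 10, 12 and 14 with the first-time convention, the estimate rose in about 50% of samples with one death and 77% with two, and fell in 0.02% or fewer. Under the midpoint convention a small share of individual samples falls, but the typical value still rises.

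A second simulation also placed progression dates on the 9-week scan grid (10 to 20 responders, 4,000 samples). Censoring deaths raised the median in 31-39% of trials at d = 10% and in 56-67% at d = 20%, and lowered it in none.

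**The case against.** The strongest reply is that the event definition already settles the matter. Death of any cause is named as an endpoint. Kaplan-Meier censoring applies to subjects without an event, so a responder who has died is not a candidate for it. The literal reading would leave the mention of death with no effect for exactly the patients it was written for. The PFS bullet points to the same intent. Appendix 1 is weak evidence the other way: it calls itself an overview of RECIST 1.1, and it also describes duration of stable disease before saying that this is not measured here.

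Most of this stands. A reader might infer that the plan will censor deaths and so will overstate duration; the documents do not support that. They support only that one sentence, read literally, says so, and that Section 14.4 does not correct it.

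A reader might also take +13% and +27%, the result for 12 responders with the first-time convention, as the size of the effect. That convention picks the 6th of 12 ordered values, so the starting value is 5.3 against an assumed truth of 6.0, and the one-death result merely returns to 6.0. Under the midpoint convention, or with 13 responders, the change is roughly half as large. With 12 responders and one death, the estimate does not move at all in 40-50% of samples.

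Finally, scans continue every 9 weeks until progression even after treatment stops (Sections 5.3, 5.5.4 and 5.9), which limits how often a confirmed responder can die without documented progression.

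**Conclusion.** The point holds as a conflict of wording with a known direction of bias. Counting deaths as events is the likely intent, but the censoring sentence as written contradicts it for responders who die without progression and is inconsistent with the PFS rule beside it.

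The size is illustrative: about 5-16% on the typical estimated median for one such death and 13-35% for two. It rests on a 6-month true median, exponential durations, 10 to 14 responders per cohort, and an assumed count of deaths. The documents supply neither the median nor the count. With no such deaths the effect is zero.

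The consequence is minor. Duration of response is a descriptive secondary endpoint with no test or decision rule attached. A reader might extend the concern to the trial's main conclusions, but ORR, sample size, power and PFS do not use this rule.

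**What to change.** - **Section 10.4:** replace the duration censoring sentence with wording parallel to PFS, for example: *Responders who die without PD are counted as events on the date of death; only responders who are alive without PD are censored, at their last tumor assessment.*
- **Appendix 1, Duration of Overall Response:** add death of any cause as an endpoint, or refer the definition to Section 10.4.

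The cost is two wording edits, made before the duration analysis is run. No new data, visits or patients are needed, and no figure in Section 14.2 changes.

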10.5. Laboratory measurements

Clinical laboratory tests will be performed at the investigational sites. Screening assessments of laboratory parameters may be used as Baseline assessments if they are performed within 3 days before the start of study treatment.

Table 4 presents the clinical laboratory tests to be performed at various time points during the study. **All results from laboratory assessments obtained at a scheduled visit must be reviewed before administration of study treatment.**

The Study Calendar (Table 3) shows the visits at which blood will be collected for clinical laboratory tests.

Hematology assessments will be performed at Screening, Day 1 and Day 8 of each treatment cycle, and the End-of-Treatment visit.

Clinical chemistry assessments will be performed at Screening, Day 1 and Day 8 of each treatment cycle, and the End-of-Treatment visit.

Table 4: Clinical Laboratory Tests

Category	Tests
Hematology^a	1. Hematocrit, hemoglobin, RBC, platelet count, WBC with differential (bands, basophils, eosinophils, lymphocytes, monocytes, neutrophils), ANC
Clinical Chemistry^b	
Screening/Baseline Panel	2. Pregnancy test (serum or urine β -hCG), chloride, potassium, sodium, BUN, serum creatinine, calcium, albumin, total protein, alkaline phosphatase, ALT, AST, total bilirubin, magnesium
Treatment Panel	3. Chloride, potassium, sodium, BUN, serum creatinine, calcium, albumin, total protein, alkaline phosphatase, ALT, AST, total bilirubin, magnesium

ALT = alanine aminotransferase; ANC = absolute neutrophil count; AST = aspartate aminotransferase; β -hCG = beta-human chorionic gonadotropin; BUN = blood urea nitrogen; RBC = red blood cells; WBC = white blood cells

a: Hematology assessments obtained at Screening/Baseline, Days 1 and 8 of each treatment cycle

b: Chemistry assessments obtained at Screening/Baseline, and Day 1 and Day 8 of each treatment cycle

10.6. Vital signs and weight measurements

Vital sign measurements (blood pressure [BP], heart rate [HR], respiratory rate, oral body temperature [$^{\circ}$ C]) and weight will be obtained at the time points designated on the Study Calendar. Height will be measured at the Screening Visit only. Weight will be recorded on Day 1 and 8 of each cycle, before the subject receives study treatment, for calculation of BSA.

10.7. Electrocardiograms

Standardized, 12-lead ECGs will be performed at Screening, Baseline, once during Cycles 1 or 2 (preferably on Day 1 of Cycle 2 before administration of study treatment), and at the End-of-Treatment visit. The Screening assessment may be used as the Baseline assessment if the ECG is performed within 3 days before the start of study treatment.

An ECG abnormality may meet AE criteria as described in Section 11 of this protocol and the CRF completion guidelines. In these instances, the AE corresponding to the ECG abnormality will be recorded on the Adverse Event page of the eCRF. For ECG abnormalities meeting SAE criteria, the study site must fax the SAE report, including the ECG report, to the Eisai Drug Safety Department using the SAE reporting form.

11. ADVERSE EVENT REPORTING REQUIREMENTS

11.1. Definitions

11.1.1. Adverse Event (AE)

An adverse event (AE) is any undesirable sign, symptom or medical condition or experience that develops or worsens in severity after starting the first dose of study treatment or any procedure specified in the protocol, even if the event is not considered to be related to the study.

Abnormal laboratory values or diagnostic test results constitute adverse events only if they induce clinical signs or symptoms or require treatment or further diagnostic tests.

